3.8 Schedule of activities

	Screening (7 days prior to rotation)	Randomization (2 days prior to rotation)	Day 2 of rotation	2-week follow-up
Review of general medical service schedule and outreach to eligible interns	X			
Completion of consent		X		
Completion of baseline questionnaire*		X		
Randomization		X		
Provision of interventions (simulation training and online education)			X	
Adverse event reporting measurement			X	X
Provision of endline (follow-up) questionnaire*				X
EHR and scheduling system data evaluation*				X

***Baseline Questionnaire (Providers):** Demographics (age, sex, race/ethnicity), 6-item State-Trait Anxiety Inventory³², 8-item Physicians' Reaction to Uncertainty Stress from Uncertainty subscale

Endline Questionnaire (Providers): 6-item State-Trait Anxiety Inventory³², 8-item Physicians' Reaction to Uncertainty Stress from Uncertainty subscale, Satisfaction with the interventions

EHR fields:

Baseline: Provider: Prior prescribing of high-risk medications; Eligible patients: Demographics (age, sex, race/ethnicity, insurance status), prior in-hospital use of one of the high-risk medications, admitted on one of the high-risk medications, hospitalization within last 30 days, total no. of home medications;

Follow-up: Prescribing of one of the high-risk medications, prescribing of albumin and other high-risk medications (e.g., opioids), discharge medication orders, administration of the one of the high-risk medications

Scheduling system (Amion®) fields:

Provider: Baseline; Prior inpatient service blocks (i.e., ICU service, ambulatory service), no. of months of internship, characteristics of the rest of the team (i.e., number of residents, seniority of attending, no. of other team members);
Follow-up: Completion of simulation training, no. of days on twilight service

4. Study Population

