5.3 Measures to minimize bias: randomization and blinding

Interns who consent will be randomized in a 1:1 ratio to receive either intervention or control using a random number generator. We plan to conduct stratified randomization based on the service to which the intern is assigned to (GMS, ITU, or Faulkner).

The providers will not be blinded to which arm to which they were assigned, as blinding in the context of an intervention that is intended to motivate action will be infeasible. Physicians randomized to control will not have any way of accessing the intervention. Of note, once on a twilight team, interns are unlikely to rotate back onto a service, so contamination across arms should be minimal. Either way, if this does happen, they will not be re-randomized in the trial. Other ward staff and analysts will be blinded to arm assignment to the extent possible.

6. Study Assessments and Procedures

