6.1 Baseline data

We will collect baseline data on providers using a brief baseline questionnaire at the time of consent as well as extracted EHR data and data from the Amion scheduling system. This baseline data will be used to assess any potential imbalances in the characteristics of providers despite randomization. The baseline data will include relevant demographic characteristics, such as age, sex, race/ethnicity, and number of months in training. Given the strong potential for characteristics of the study team to influence outcomes, despite randomization, we will also measure characteristics about the interns' team using the Amion scheduling system. Finally, we will also collect patient data from the EHR for eligible patients in follow-up (please see the footnote Section 3.8 for more detail).

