7.3 Statistical analyses

7.3.1 *Analysis of the primary endpoint*

The unit of analysis is at the patient-level. We will evaluate the primary outcome using generalized estimating equations to adjust for physician-level clustering and multiple patient-day observations per physician using a log-link function, Poisson-distributed errors, and fixed effects for the treatment group and month of the year to account for seasonality. This approach will account for correlations between repeated measurements. Because this is a randomized trial, our primary analyses are planned as unadjusted; however, if there are strong predictors of the outcomes not balanced by stratified randomization, we will adjust for these in the primary analyses. We will conduct analyses using intention-to-treat principles. Given the nature of the data and how the outcomes are measured in EHR data, there will not be missing data for the primary outcome.

7.3.2 *Analysis of secondary endpoints*

We will use a similar approach for the secondary outcomes. For discharge medication orders (secondary outcome), we will also use generalized estimating equations that adjust for physician-level and patient-level clustering using a logit-link function, binary-distributed errors, and fixed effects for the treatment group and month of the year. For the outcomes measuring spillover

effects, the approach will be the same, except using a log-link function and Poisson-distributed errors. Given the nature of the data and how these outcomes are being measured primarily in EHR data, there should not be missing values. Because this is a randomized trial, our primary analyses are planned as unadjusted; however, if there are strong predictors of the outcomes not balanced by randomization, we will adjust for these in the primary analyses.

The implementation outcomes will be measured at the provider-level. The characteristics of consenting and non-consenting physicians will be measured descriptively, comparing the values using t-tests and chi-square tests or non-parametric analogs, as appropriate. Other implementation outcomes will be measured descriptively.

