7.3.3 Baseline descriptive analyses

We will report the means and frequencies of pre-randomization variables separately for intervention and control subjects. Comparisons of these values will be performed using t-tests and chi square tests and their non-parametric analogs, as appropriate. The outcomes will be evaluated using intention-to-treat principles among all randomized patients.

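### The primary model adds covariates only on an undefined imbalance trigger; fix the covariate set, with a small-sample standard error, before outcome data are extracted

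*Combined protocol and SAP*

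**What the plan says.** Section 7.3.1 specifies a Poisson log-link GEE with "fixed effects for the treatment group and month of the year to account for seasonality". It calls the primary analysis unadjusted but adds the exception "if there are strong predictors of the outcomes not balanced by stratified randomization, we will adjust for these in the primary analyses". Section 7.3.2 has the same exception: "if there are strong predictors of the outcomes not balanced by randomization, we will adjust for these in the primary analyses".

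Other sections bear on the exception without defining it:

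- Section 5.3 sets the strata: "We plan to conduct stratified randomization based on the service to which the intern is assigned to (GMS, ITU, or Faulkner"). Service is not among the stated model terms.
- Section 3.8 lists "Provider: Prior prescribing of high-risk medications" among the baseline EHR fields, beside many patient and team fields. It is not a model term either.
- Section 6.1: "This baseline data will be used to assess any potential imbalances in the characteristics of providers despite randomization".
- Section 7.3.3: "Comparisons of these values will be performed using t-tests and chi square tests and their non-parametric analogs, as appropriate". No threshold is given, and nothing links these tests to the model.
- Section 3.2 states analyst blinding without qualification; section 5.3 softens it: "Other ward staff and analysts will be blinded to arm assignment to the extent possible".

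**The concern.** Two analysts following section 7.3.1 faithfully could report different primary models, because the plan does not say how strong a predictor must be, how imbalanced, who judges this, or when. Masked arm labels hide the direction of an effect but not its p-value, so blinding narrows the room for choice without closing it.

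The trigger also asks the wrong question. Adjusting for a prognostic baseline variable gains precision whether or not it happens to be imbalanced. A trigger therefore recovers only part of the available gain, and with few randomized units intern-level covariates are where most of that gain lies. Balancing on service by design and then omitting it from the model leaves the standard error too large if service predicts prescribing.

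**Working it through.** **1. The plan's own power figure.** Section 7.2 gives 36 interns (18 per arm), 430 patients, 1290 patient-days, difference 0.5, SD 1.1, correlation 0.2, and cluster size 12 patients or 36 patient-days. The correlation is read as within intern, which is an assumption. The design effect is 1 + (m - 1) x 0.2.

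- Patient-days: 1 + 35 x 0.2 = 8.0; 645 / 8.0 = 80.6 effective per arm; SE = 1.1 x sqrt(2 / 80.6) = 0.173; power = Phi(0.5 / 0.173 - 1.96) = about 82% (80.1% with t on 34 df). The stated figure of over 80% reproduces.
- Patients: 1 + 11 x 0.2 = 3.2; 215 / 3.2 = 67.2; power 75.0% (72.6% with t).

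This calculation uses no covariates, so the trigger does not affect it.

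**2. Where the variance lies.** The between-intern share of the variance of an intern mean is ICC / (ICC + (1 - ICC) / m). At ICC 0.2 it is 0.2 / (0.2 + 0.8/12) = 75% and 0.2 / (0.2 + 0.8/36) = 90%. At ICC 0.1 it is 57% and 80%.

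**3. How a trigger behaves.** With a cut-off of p < 0.05, a given covariate enters in about 5% of trials; with a cut-off of 0.25 SD, in about 45%. At least one of 10 independent baseline tests reaches p < 0.05 by chance with probability 1 - 0.95^10 = 40%.

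**4. Type I error.** Simulated with linear models on 36 intern means, nominal 5%, with the number and strength of candidate covariates assumed:

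| Rule | Type I error |
|---|---|
| Treatment + month | 4.2-5.4% |
| Trigger applied mechanically at >0.25 SD | 3.0-4.5% |
| Covariate set fixed in advance | 4.4-5.4% |
| Smaller p of the unadjusted and triggered models | 5.6-7.4% |
| Most favourable of several cut-offs (separate simulation) | 5.5-7.1% |
| Treatment + month when service explains 20% of between-intern variance | about 3-3.6% |

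**5. Power.** Treatment + month against the same model plus service and prior prescribing. Assumed layout: 12 interns per service split 6:6, and six interns in each of six months; 4,000 runs per cell. r is the correlation of prior prescribing with the intern's true prescribing level. Service explains nothing in these rows.

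| ICC, r | 12 patients | 36 patient-days |
|---|---|---|
| 0.2, r = 0 | 65.3 to 63.1% | 73.6 to 70.6% |
| 0.2, r = 0.3 | 64.2 to 64.8% | 73.6 to 74.8% |
| 0.2, r = 0.5 | 65.3 to 72.0% | 74.6 to 82.5% |
| 0.1, r = 0.3 | 83.1 to 82.4% | 92.7 to 92.8% |
| 0.1, r = 0.5 | 83.0 to 86.0% | 92.4 to 95.9% |

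At ICC 0.2 and r = 0.5, a trigger at >0.25 SD reaches only 68.6% and 78.7%. If service explains 20% of between-intern variance, adding service alone is worth about 5-6 points. The starting values lie below step 1 because of the month terms; without month and service terms the simulation gives 72.7% and 80.0%, which agrees with the t-based figures there.

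A Poisson check (assumed control rate 1.0, rate ratio 0.6, hence a difference of 0.4 and not 0.5; leverage-corrected standard errors; ICC 0.2) gives 67.1 to 71.1% and 75.0 to 82.2% at r = 0.5. At r = 0.3 it gives 65.6 to 65.4% and 75.2 to 77.3%.

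**6. Standard errors.** With six month levels, intern-level degrees of freedom are 36 - 1 - 1 - 5 = 29. Service takes 2 and prior prescribing 1, leaving 26. Section 7.3.1 names no standard error. Under the null, a Poisson model with an ordinary uncorrected sandwich and z-test gives 9.3-11.3% for treatment + month and 11.6-13.8% for the larger set across the settings tried. With a leverage correction the figures are 5.2-5.6% and 5.3-5.5%.

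**The case against.** The case for leaving the clause alone has four parts.

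*Harm is limited.* The stated model is valid, analysts are to be blinded, and section 7.2 presents the trial as a pilot. This stands. A reader might infer that the trigger itself inflates type I error or invalidates the primary test. The documents do not support that: applied mechanically, it makes the test conservative. Inflation requires someone to choose after seeing results. Free choice of the single most favourable covariate would give 5.9-11.4%, but the clause ties adjustment to imbalance and does not license that choice.

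*The precision gain is assumed.* Neither r nor the service effect is in the documents, and section 7.2 calls 0.2 conservative, so a lower correlation is possible. Under section 4.3 an intern's twilight assignment does not repeat, so prior prescribing comes from other services and may be sparse early in training. This also stands. A reader might infer an assured gain in power; none can be promised.

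*Prior prescribing brings its own open choices.* Its window and denominator are undefined, and section 3.8 schedules EHR evaluation at the 2-week follow-up, so on that schedule it would be extracted alongside the outcomes. This is a reason to settle those choices early and to have a fallback.

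*More terms can worsen the test.* Step 6 bears this out if the sandwich is left uncorrected. The correction must therefore accompany the covariate set, and the plan's own model needs it too.

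None of this supplies the missing cut-off or decision time.

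**Conclusion.** The point holds as a prespecification defect with a conditional efficiency cost. It is not a sample-size error and does not invalidate the treatment-plus-month model. The worst-case type I error from choosing between models by p-value is roughly 5.5-7.5%, limited by blinding.

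At a within-intern ICC of 0.2, the fixed set changes power as follows:

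- about +6 to +8 points if r is 0.5 (about 4 to 7 in the Poisson check);
- about +5 to +6 from service alone if it explains 20% of between-intern variance;
- about 0 to +1 at r = 0.3 with no service effect;
- about -2 to -3 if neither variable predicts the outcome.

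At ICC 0.1 the change is about -1 to +3.5 points for r of 0.3 to 0.5 with no service effect.

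These figures rest on the assumed layout, on reading the 0.2 in section 7.2 as within intern, and mainly on linear models of intern means in place of the Poisson GEE. They show direction and rough size. The prespecification argument does not depend on them.

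**What to change.** In sections 7.3.1 and 7.3.2:

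1. Delete the imbalance trigger. Before outcome data are extracted, fix the model terms: treatment, month, service stratum (GMS, ITU or Faulkner) and the intern's pre-randomization high-risk prescribing rate. Fixing them only before unblinding would be too late, because p-values can be seen under masked labels.
2. At the same time, fix that rate's look-back window, denominator and rule for interns with little or no prior data. If a blinded check before outcome extraction shows the data are too sparse, keep month and service only.
3. Name a small-sample correction for the GEE: a bias-corrected sandwich with a t reference on intern-level degrees of freedom.
4. Use the same set for the discharge-order and spillover models, and state that the discharge odds ratio is conditional on these covariates.
5. Report treatment plus month, and any adjustment for other imbalanced variables, as sensitivity analyses only. Keep in-hospital exposure before the intern's care in the stratified analyses of section 4.

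Cost: SAP wording, plus pulling the prior-prescribing field ahead of the outcomes. No new data are collected. Intern-level degrees of freedom fall from 29 to 26 (25 with a sparse-data indicator), and about 2-3 power points are lost if neither added variable predicts prescribing.

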7.3.3 Baseline descriptive analyses

We will report the means and frequencies of pre-randomization variables separately for intervention and control subjects. Comparisons of these values will be performed using t-tests and chi square tests and their non-parametric analogs, as appropriate. The outcomes will be evaluated using intention-to-treat principles among all randomized patients.

7.3.4 Subgroup analyses

In subgroup analyses, we will explore whether there were any modifiers of the effects of the simulation-based intervention. For example, we will explore if the intervention effectiveness differed by month of the year, whether there were team-level differences, or if there were observable differences in patients who were less likely to receive high-risk medications, such as gender or race/ethnicity.

8. Ethical and regulatory requirements

8.1 Ethical conduct

General oversight of the project by the principal investigators (Drs. [name] and [name]) will occur throughout the study period, including regular contact with clinical leadership to obtain ongoing feedback. In addition, this protocol will be overseen by the MGB Institutional Review Board (IRB). Study data will be accessible at all times for the principal

investigators and co-investigators to review, if applicable. The principal investigators will review study conduct (e.g., protocol deviations) on a monthly basis. The principal investigators will also ensure that all protocol deviations for the trials are reported to the NIH and the IRB according to the applicable regulatory requirements.

We believe that the risks to participation for both sets of subjects (i.e. providers and patients) are no more than minimal for several reasons. We believe there is no more than minimal risk involved to the provider subjects, as the providers will simply undergo training to alter their behaviors towards guideline recommended care, as opposed to being forced to do so. The intervention is delivered as a simulation training that incorporates information already available to providers

In terms of patient-subjects, the intervention aims to emphasize guideline-recommended information for providers to assist in their decision-making when caring for older patients who have been admitted to the general medicine service. All treatment decisions will ultimately be made by licensed health care providers.

Patient data to inform the study and conduct evaluations will be drawn from EHR data maintained by the health systems. We will also safeguard any identifiable information in accordance with IRB practices, limit access to any information in accordance with IRB practices, limit access to the information to study investigators actively involved in the research who have all undergone human subjects research training, and destroy any data upon completion of the research. Finally, as is our routine practice, throughout this work, great care will be taken to ensure the confidentiality of all data and to protect the privacy of participants through translation of all potentially traceable identifiers into untraceable coded subject numbers.

8.2 Informed consent

Interns will be eligible if they are scheduled to work for one of the general medicine service wards during an evening block on one of the “twilight” teams.

We request a waiver of documentation of informed consent and will obtain e-consent without a signature requirement. We believe this waiver is justified for this study for several reasons. First, the subjects being intervened upon are physicians at BWH/BWFH and the study team will

not have any contact with patients. The proposed intervention being tested is very similar to existing quality improvement initiatives already offered at BWH and intends to evaluate interventions to encourage physicians to follow care processes based on widely-accepted clinical practice guidelines. The interventions involve providing them with tools to improve prescribing in accordance with these guidelines and they can ignore this guidance. Additionally, a formal written informed consent process would be infeasible for this study. Interns are busy and the components of this intervention are very familiar to them; therefore, the standard consent process would be burdensome and likely be a barrier to study enrollment. If we have difficulty recruiting sufficient interns for the study, and therefore unable to reach our sample size targets, our study will be insufficiently powered. Further, if we have highly self-selected sample, this can bias our results and make them less generalizable.

Instead, after reviewing the information sheet that we will electronically provide to potential participants and prior to their agreeing to participate, subjects will be invited to talk with the study team by phone or Zoom to address questions or concerns, and our contact information will be easily accessible for potential participants. For these reasons, we feel that a waiver of documentation of informed consent with the option for video or phone conversation for any questions or concerns would be the best consent process for this study. We also have approval from clinical leadership and chief residents for this approach. Finally, the surveys as part of this study take only 10-15 minutes, are all validated and widely used, and PCPs will be compensated for their time.

We will obtain e-consent with a waiver of written consent (signature) and waiver of documentation of informed consent for participation in the trial through e-consent documentation in REDCap, a secure HIPAA-compliant web-based platform hosted on our Mass General Brigham servers. Intern physician subjects will be invited to participate via email. The information sheet below will be attached to the email, and contains information about the study, their participation, and the names and contact information for study staff who can be reached for a phone or video conversation if they have any questions or concerns. We have received approval from clinical leadership for this approach. Interested intern physicians will be asked to click on a link in the email to open a secure RedCap survey. There, interns will again view an electronic copy of this information sheet. If the physician agrees to participate, he or she will click a button indicating "I agree". E-consent documentation (without signature or documentation of written consent) will be captured in REDCap, which is a secure, HIPAA-compliant web-based platform hosted on the MGB servers. We will provide sufficient information to the prospective provider-

subjects about the nature of the study and their rights within the fact sheet, as well as provide contact information for study staff and IRB for any additional questions.

BWH study staff and data analysts will track any physician turnover in the study using the Amion electronic residency scheduling system and the paging directory. While minimal turnover before the end of the block is expected, we expect any turnover to bias the trial results towards the null. If providers wish to revoke their consent and no longer participate in the study, they will also be removed from the study.

We also request a waiver of patient informed consent and authorization for the collection of routinely-collected patient data for outcome evaluation, given the minimal risk nature of the study, as we have done in prior work. We believe this waiver is justified as investigators will have no direct patient contact and all prescribing decisions are made under the care of licensed physicians, including supervising residents and attending who are directing their care. Finally, the intervention is exclusively provider-facing with the underlying goal of promoting patient safety in accordance with clinical practice guidelines.

